4. Exploratory Aim 4: Test the hypothesis that exposure to one week of sleep restriction with concurrent exposure to extended duration ALAN (LD 19:5) will lead to a greater reduction in the levels of long-chain highly unsaturated triglycerides than exposure to one week of sleep restriction without extended duration ALAN (LD 14:10). Plasma lipids will be assessed via mass spectrometry for a baseline and sleep-restricted sample from each participant in the above studies under ALAN and non-ALAN conditions. Because lower levels of long-chain highly unsaturated triglycerides are associated with a loss of insulin sensitivity [30], we will assess whether sleep restriction with ALAN leads to adverse changes in the levels of these triglyceride species that do not occur when sleep restriction is conducted without ALAN.
5. Exploratory Aim 5: test the hypothesis that exposure to one week of sleep restriction with concurrent exposure to extended duration ALAN (LD 19:5) will lead to a difference in the exhaled VOC profile compared with exposure to one week of sleep restriction without extended duration ALAN (LD 14:10).

6. Exploratory Aim 6: test the hypothesis that exposure to one week of sleep restriction with concurrent exposure to extended duration ALAN (LD 19:5) will lead to a change in the proteomic profile compared with exposure to one week of sleep restriction without extended duration ALAN (LD 14:10).
7. Exploratory Aim 7: test the hypothesis that the BodyTime assay will track changes in the melatonin profile and show a change in timing after exposure to one week of sleep restriction with concurrent exposure to extended duration ALAN (LD 19:5) compared to baseline.
8. Exploratory Aim 8: test the hypothesis that exposure to one week of sleep restriction will induce changes in objective human vocal parameters, both with and without extended duration ALAN.

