**Analysis of voice recording (Exploratory Aim 8).** Human vocal parameters will be collected during specified wake times. Power spectral density, intensity, pauses, reading mistakes, and automatic speech recognition (ASR) system errors are extracted from each audio file containing one sentence recording. These features will be aggregated at various scales (over each list or subject). Different acoustic analysis techniques and computer programs will be used to extract these features in a retrospective manner. The table below lists our proposed features.

Feature	Note
Duration (seconds) and percentage of voiced segments	
Duration (seconds) and percentage of vocalic segments	
Number, duration (seconds), and location of pauses	Natural and unnatural pauses
Reading mistakes (counts)	Stumbling, paralexia, deletion, and addition
ASR errors (counts)	
Power spectral density (square of amplitude)	Mean, variance, min, max, and slope
Intensity analysis (decibel)	Mean, variance, min, max, and slope
Jitter (seconds), shimmer (seconds), and HNR (%)	Provided by the Praat Software

After preprocessing and extraction, vocal features will be decorrelated with confounding factors, including age, sex, BMI, and other demographic information of subjects. Any feature correlated to confounding factors will be replaced by the residue of a multivariate linear regression approximating the value of the feature from confounding factors. One-way ANOVA will be performed to examine if vocal features are significantly different between recordings from different sleep-wake conditions (baseline, restricted sleep with extended duration ALAN, and restricted sleep without extended duration ALAN). Mann-Whitney U tests will be performed to compare between conditions. For repeated vocal parameter measurements during the same experimental segment, they will be aggregated and averaged over the segment duration to achieve global-level comparison.

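### Exploratory Aim 8 tests one hypothesis on 22 to 28 vocal features with no lead feature, multiplicity control or success rule

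*Combined protocol and SAP*

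**What the plan says.** Section II words Exploratory Aim 8 as a test: sleep restriction "will induce changes in objective human vocal parameters, both with and without extended duration ALAN". The aim therefore claims a change in each of the two sleep-restriction conditions. It does not say which vocal parameter carries the claim.

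Section VI, Analysis of voice recording, introduces the outcomes with "The table below lists our proposed features". The table has eight rows, several holding more than one measure, for example "Number, duration (seconds), and location of pauses", and "Mean, variance, min, max, and slope" for each of two signals. For the tests it states "One-way ANOVA will be performed to examine if vocal features are significantly different between recordings from different sleep-wake conditions", the conditions being baseline, restriction with ALAN and restriction without ALAN. It then adds "Mann-Whitney U tests will be performed to compare between conditions". Repeated measurements within a segment are averaged.

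For Aim 8 the document gives no significance level, lead feature, multiplicity adjustment or success rule. It does not say whether the pairwise tests depend on a significant ANOVA.

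**The concern.** One hypothesis is examined through many outcomes, and nothing says how many must be significant, or which. An analyst who finds one significant feature among 22 to 28 could report the aim as supported, and the plan would offer no ground to object. The chance that at least one feature is significant with no true effect can be far above 5%, so a positive statement about the voice would carry little information. What is at stake is the interpretation of one exploratory aim. No primary outcome is touched.

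**Working it through.** **Plan's own figure.** There is none for Aim 8. The nearest are in the power section: 0.05/3 = 0.0167 for the three primary outcomes and 0.05/2 = 0.025 for the two Exploratory Aim 4 outcomes. Both divisions are correct, but neither applies to Aim 8.

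**Inputs from the document.** 20 participants (section III); a within-subjects crossover (section IV); three conditions, hence three possible pairs (section VI; the number of pairs is inferred).

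**Feature count, by table row.**
- Minimum: 2 (voiced) + 2 (vocalic) + 3 (pauses) + 1 (reading mistakes) + 1 (ASR errors) + 5 (spectral) + 5 (intensity) + 3 (jitter, shimmer, HNR) = 22.
- With pauses split into natural and unnatural (6) and mistakes split by type ("Stumbling, paralexia, deletion, and addition", 4): 2 + 2 + 6 + 4 + 1 + 5 + 5 + 3 = 28.

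**Assumed, because the document gives no value.** A level of 0.05 per test; between-feature correlation r from 0 to 0.8; where needed, within-person correlation (ICC) across conditions.

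**Step 1: independent features, valid omnibus tests.** The chance of at least one false positive is 1 − 0.95^k.
- k = 22: 1 − 0.95^22 = 67.6%
- k = 28: 1 − 0.95^28 = 76.2%

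The expected number of false positives is 22 × 0.05 = 1.1 to 28 × 0.05 = 1.4. This expectation does not depend on the correlation between features.

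**Step 2: correlated features, tests that respect the pairing.** Simulation with no true effect: 20 people, three conditions, repeated-measures F (2 and 38 df) and paired t-tests at 0.05, 2,000 replicates. Entries are for 22 / 25 / 28 features.

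| r | any false omnibus | any false omnibus or pairwise |
|---|---|---|
| 0 | 68 / 74 / 75% | 95 / 97 / 97% |
| 0.5 | 47 / 48 / 52% | 80 / 81 / 84% |
| 0.8 | 25 / 27 / 28% | 50 / 52 / 54% |

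The last column counts pairwise tests whether or not the ANOVA is significant. With Benjamini-Hochberg at 5% across the omnibus tests, the chance of any false rejection was about 1% to 6% over these scenarios.

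**Step 3: the tests as written, on segment means.** One-way ANOVA and Mann-Whitney treat the three conditions as separate groups. Person-to-person variance stays in the ANOVA error term but cancels from the condition contrasts, so the real level falls as ICC rises: about 2.0% per ANOVA at ICC 0.25, 0.4% at 0.5 and below 0.1% at 0.75. With independent features (22 to 28):

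| ICC | any false omnibus | any false omnibus or pairwise |
|---|---|---|
| 0.25 | 36 to 43% | 77 to 84% |
| 0.5 | 9 to 11% | 38 to 49% |
| 0.75 | below 1% | about 5% |

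**Step 4: the aim taken literally.** With valid paired tests at 0.05, the chance that some single feature falsely differs from baseline in both restriction conditions is about 5% to 22%, falling as r rises.

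**The case against.** The best defence has four parts.

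1. *The aim is a feature screen.* It is labelled exploratory, section V says only that the speech task may be given, and no power is claimed. The plan also leaves its lipid screen (more than 600 detectable lipids, section V, Plasma lipidomics) without adjustment. This stands as a reason for low priority. It also means that the 0.025 for Exploratory Aim 4 cannot be read as a policy of controlling exploratory aims: that figure occurs only in a power statement for two named outcomes.

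2. *The tests as written are conservative on segment means.* Step 3 confirms this. But that protection comes from ignoring the pairing, and it disappears once valid tests are used. It also depends on the unit of analysis. Section VI mentions aggregation over lists as well as over subjects, and a list-level ANOVA can err in the other direction. With subject variance of 40% to 50% and subject-by-condition variance of 5% to 20% (both assumed), 14 lists per segment gave a per-test error of 9% to 42%. With no subject-by-condition variance it stayed below 1%.

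3. *The aim requires a change with and without ALAN.* An isolated omnibus result, or a difference between the two restriction conditions, does not establish that. This stands, and Step 4 shows the much smaller rate. But section VI does not tie the conclusion to this reading.

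4. *Pairwise tests after an ANOVA are often follow-ups only.* The document is silent, so it cannot be said that they are planned regardless of the ANOVA. If they are follow-ups, the omnibus column in Step 2 is the relevant one.

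**Conclusion.** The omission is real: 22 to 28 features, an omnibus test and between-condition tests, and no rule linking them to the single hypothesis. At an assumed 5% per test, with tests that respect the pairing, the chance of at least one false omnibus result is about 25% to 75%. It is about 50% to 97% if pairwise tests count regardless of the ANOVA.

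A reader might infer that, under the plan as written, a false voice finding is more likely than not. The documents do not support this. They give no significance level for Aim 8 and no between-feature or within-person correlation, and several features summarise the same signal and may be strongly correlated. With the written tests on segment means, every simulated rate was below 50% at ICC 0.5 and at most about 6% at 0.75. On the aim's literal wording, the same-feature rate is about 5% to 22% even with valid tests.

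This is a minor point about what an exploratory aim may conclude.

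**What to change.** In section VI, Analysis of voice recording:

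- Replace the independent-groups tests with paired or mixed-model tests on segment means. Do this together with the multiplicity rule: once the tests hold their nominal level, the rates in Step 2 apply in full.
- List the features to be tested and apply Benjamini-Hochberg at 5% across their omnibus tests.
- Run the three pairwise comparisons only for features that pass, with Holm adjustment across the three.
- State that Aim 8 is supported only if a surviving feature differs from baseline in both sleep-restriction conditions, as section II words it.

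Alternatively, name one or two key features for the aim and label the rest descriptive.

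The cost is a few sentences in the analysis section and a small change to the code. No new data are needed and no primary analysis changes. The drawback is some loss of power for single features.

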## II. SPECIFIC AIMS

The goal of this project is to evaluate whether extended duration ALAN contributes to the adverse effects of sleep restriction on glucose metabolism. We plan to use a crossover design consisting of a 7-day baseline, 7-day sleep restriction (to 5h per night) with (LD 19:5) or without (LD 14:10) ALAN, 9-day washout, and another 7-day sleep restriction with or without ALAN (Figure 8). 20 healthy participants will be randomly assigned to receive ALAN in either the first or second exposure, balanced by age and sex. Specifically, we plan to:

1. Test the hypothesis that exposure to one week of sleep restriction with concurrent exposure to extended duration ALAN (LD 19:5) will induce greater impairment of insulin sensitivity than exposure to one week of sleep restriction without extended duration ALAN (LD 14:10). Insulin sensitivity (SI) will be assessed via an intravenous glucose tolerance test (ivGTT) before and after each week of exposure.
2. Test the hypothesis that exposure to one week of sleep restriction with concurrent exposure to extended duration ALAN (LD 19:5) will induce greater impairment of glucose tolerance than exposure to one week of sleep restriction without extended duration ALAN (LD 14:10). The 90-minute glucose area under the curve (AUC) will be assessed in response to a standardized meal both before and after each week of exposure.
3. Test the hypothesis that exposure to one week of sleep restriction with concurrent exposure to extended duration ALAN (LD 19:5) will reduce the duration of nocturnal melatonin secretion as compared to baseline more than exposure to one week of sleep restriction without extended duration ALAN (LD 14:10). The 24-h profile of melatonin secretion will be assessed during the lighting conditions that prevail throughout both sleep restriction conditions (i.e., 5h in darkness per night vs. 10h in darkness/near darkness per night). To determine the mechanism of this anticipated decrease in the duration of melatonin secretion (acute light-induced melatonin suppression vs. a reduction in the duration of the endogenous melatonin secretory profile), we will also measure the endogenous melatonin secretory profile on a ~24-hr recording on the day immediately after each week of intervention.

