## **V. STUDY PROCEDURES**

The experimental protocol consists of 6 segments: ambulatory baseline; laboratory baseline assessment of glucose metabolism and circadian rhythms; first sleep intervention including re-assessment of glucose

Detailed Protocol, version 11

Page 6

May 23, 2023

metabolism and circadian rhythms; washout followed by second baseline assessment of glucose metabolism and circadian rhythms; second sleep intervention including re-assessment of glucose metabolism and circadian rhythms, and recovery. The ambulatory baseline is roughly 2 weeks, after which participants will be studied in the laboratory for a 33-day protocol.

During the **Ambulatory Baseline**, wrist activity and light levels will be recorded in participants at home for approximately 2 weeks prior to study admission. They will be asked to wear an activity monitor (MotionWatch 8 or similar, CamNTech, Inc.) on the wrist of the non-dominant hand, maintain a regular self-selected sleep-wake schedule with 9h time in bed each night, record this schedule in a sleep diary, and call in to our time-stamped call-in telephone system just prior to each bedtime and immediately after each wake time. These procedures will ensure the participants are stably entrained to their schedule and well-rested when the study begins. We may also ask them to log the time, content, and amount of food and drink consumed each day during this time in a food diary. This will inform us of the participant's usual diet and allow comparison with the laboratory diet.

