The speech of the subjects will be recorded by a Shure VP64A omnidirectional microphone or equivalent (frequency response: 50 to 12,000 Hz) mounted on a desktop microphone stand. The microphone is connected to the computer via a USB to XLR adapter and cord extensions. The height and horizontal extension of the stand are adjusted to hold the microphone close to the lips of the subject when sitting at the desk in their study room in the lab. The microphone is covered by a standard windscreen.

While previous studies used different text corpora and languages when recording human voice, most have emphasized phonemically balanced texts [Bagnall AD, Dorrian J, Fletcher A. Some Vocal Consequences of Sleep Deprivation and the Possibility of "Fatigue Proofing" the Voice With Voicecraft® Voice Training. Journal of Voice. 2011;25(4):447-461. doi:10.1016/j.jvoice.2010.10.020; Icht M, Zukerman G, Hershkovich S, et al. The "Morning Voice": The Effect of 24 Hours of Sleep Deprivation on Vocal Parameters of Young Adults. Journal of Voice. 2020;34(3):489.e1-489.e9. doi:10.1016/j.jvoice.2018.11.010; Amato F, Rechichi I, Borzi L, Olmo G. Sleep Quality through Vocal Analysis: a Telemedicine Application. In: 2022 IEEE International Conference on

Pervasive Computing and Communications Workshops and Other Affiliated Events (PerCom Workshops). IEEE; 2022:706-711. doi:10.1109/PerComWorkshops53856.2022.9767372] and vowel pronunciations [Barron DS, Heisig S, Agurto C, et al. Feasibility Analysis of Phenotype Quantification from Unstructured Clinical Interactions. Computational Psychiatry. 2022;6(1):1. doi:10.5334/cpsy.78; Rahman W, Lee S, Islam MS, et al. Detecting Parkinson Disease Using a Web-Based Speech Task: Observational Study. J Med Internet Res. 2021;23(10):e26305. doi:10.2196/26305]. Thus, our speaking task involves reading one list from the Harvard sentences [IEEE Recommended Practice for Speech Quality Measurements. IEEE Trans Audio Electroacoust. 1969;17(3):225-246. doi:10.1109/TAU.1969.1162058] each time. There are 72 lists of Harvard sentences, each containing 10 sentences. The computer program will pick a distinct list from the corpus every time the speech task is performed so subjects do not become familiar with the text and degrade their pronunciation by reading too fast or rumbling.

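### Exploratory Aim 8 compares voice features from the same crossover participants with tests for independent groups; on segment averages this is conservative and loses power for modest effects

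*Combined protocol and SAP*

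**What the plan says.** Under Analysis of voice recording (Exploratory Aim 8) in Section VI, the overall test is: "One-way ANOVA will be performed to examine if vocal features are significantly different between recordings from different sleep-wake conditions". The conditions are baseline, restricted sleep with extended ALAN and restricted sleep without it. The follow-up is: "Mann-Whitney U tests will be performed to compare between conditions". The paragraph contains no subject term, repeated-measures version or signed-rank test.

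The design is within-person. Section II states that "20 healthy participants will be randomly assigned to receive ALAN in either the first or second exposure", Section IV calls the study a within-subjects randomized crossover, and Section V has each person undergo the remaining restriction condition in the second intervention. Section V also provides a "washout followed by second baseline assessment of glucose metabolism and circadian rhythms", so there are two baseline segments. The Aim 8 paragraph does not say how both enter the comparison.

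Several wordings bear on the unit of analysis. Features "are extracted from each audio file containing one sentence recording". Then: "These features will be aggregated at various scales (over each list or subject". The ANOVA sentence speaks of recordings. The closing sentence says of repeated measurements within a segment that "they will be aggregated and averaged over the segment duration to achieve global-level comparison".

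The opening of Section VI plans paired t-tests or signed-rank tests, and mixed models, for a named list: insulin sensitivity, AIRg, glucose effectiveness, glucose AUC, insulin AUC and melatonin duration. Voice features are not on it.

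**The concern.** One-way ANOVA and Mann-Whitney U treat the values in the three conditions as coming from different people. Here they come from the same people, and a voice has stable personal characteristics. The planned regression on age, sex, BMI and other demographics removes only the part that those variables explain. The rest stays in the error term of an unpaired test, although it cancels in a within-person comparison.

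Modest voice changes could therefore be missed that the same data would show under a paired analysis. The plan already uses paired methods for its main outcomes and, in the power section, for Exploratory Aim 4. It gives no reason for Aim 8 to differ.

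**Working it through.** **Nothing to reproduce.** The documents give no alpha, power, effect size, SD or correlation for Aim 8.

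**Inputs.** From the documents: 20 participants, three conditions, all within person. Assumed: all 20 contribute voice data, two-sided 5%, normal data with unit variance, and equal within-person correlation ρ of 0, 0.3, 0.5 or 0.7. The range starts at 0 because the demographic adjustment lowers ρ by an unknown amount.

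**Direction on segment averages.** For one value per person per condition, the difference between two condition means has true variance 2σ²(1 − ρ)/n. An unpaired analysis takes it as 2σ²/n. The ratio of true to assumed variance is 1 − ρ, that is 1, 0.7, 0.5 and 0.3. Below 1, the test is conservative.

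**Size on segment averages, by simulation.**

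| | ρ = 0 | 0.3 | 0.5 | 0.7 |
|---|---|---|---|---|
| Type I error, Mann-Whitney | 5.0% | 2.1% | 0.9% | 0.1% |
| Type I error, signed-rank | 4.9% | 4.9% | 4.9% | 4.9% |
| Type I error, one-way ANOVA | 5.0% | 1.6% | 0.4% | <0.1% |
| Power 0.5 SD, Mann-Whitney | 32% | 29% | 27% | 24% |
| Power 0.5 SD, signed-rank | 31% | 42% | 54% | 76% |
| Power 0.5 SD, one-way ANOVA | 34% | 28% | 24% | 18% |
| Power 0.5 SD, repeated-measures ANOVA | 33% | 45% | 60% | 82% |
| Power 0.8 SD, Mann-Whitney | 67% | 69% | 72% | 77% |
| Power 0.8 SD, signed-rank | 65% | 80% | 91% | 99% |
| Power 1.0 SD, Mann-Whitney | 85% | 89% | 92% | 96% |
| Power 1.0 SD, signed-rank | 83% | 94% | 98% | >99% |

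For ANOVA power, both restriction conditions are shifted equally from baseline. At 1.0 SD and positive ρ, the loss against signed-rank is 4 to 7 points; at 1.2 SD it is at most 1.5 points.

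**Two baselines as separate rows.** The conservative direction assumes one value per condition. With both baselines entered as rows, one-way ANOVA type I error was 0.005 to 0.015 at a person variance share of 0.5 and 0.047 at a share of 0.2. It was 0.082 with no person variance but correlated baselines.

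**Unaveraged recordings.** With m recordings per person per condition and variance components v_s (person), v_sc (person-by-condition) and v_e (residual), the ratio of true to assumed variance is (m·v_sc + v_e)/(v_s + v_sc + v_e). Take m = 10 and v_s = 0.5, both assumed:
- v_sc = 0, v_e = 0.5: ratio 0.5/1 = 0.5; simulated Mann-Whitney type I error 0.016.
- v_sc = 0.1, v_e = 0.4: ratio (1.0 + 0.4)/1 = 1.4; simulated Mann-Whitney type I error 0.106.

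So the error can go either way. The documents fix neither v_sc nor m. Section V says "There are 72 lists of Harvard sentences, each containing 10 sentences", but not how many speech tasks are given per segment.

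**Check of the remedy.** With four segment averages per person and a 0.5 SD shift, a model with subject, condition and period has power 48, 64, 79 and 96% at ρ = 0, 0.3, 0.5 and 0.7. One-way ANOVA on the same 40, 20 and 20 values has 49, 45, 43 and 40%. Null rejection is 5.2, 4.8, 4.9 and 4.7% for the model.

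**Number of tests.** The feature table gives about 2 + 2 + 3 + 1 + 1 + 5 + 5 + 3 = 22 features. With three pairwise comparisons, 22 × 3 = 66 tests. With no true effects, paired tests at 5% give 66 × 0.05 = 3.3 expected false positives. Mann-Whitney gives 66 × 0.0213 = 1.4, 66 × 0.0085 = 0.6 and 66 × 0.0014 = 0.1 at ρ = 0.3, 0.5 and 0.7.

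**The case against.** The best defence is that the plan errs on the safe side. The closing sentence of the Aim 8 paragraph comes directly after the two tests and describes averaging over the segment. Read naturally, the tests use segment averages and reject too rarely. For an exploratory screen of many features, low false-positive rates are no great harm. This stands, and it sets the importance of the point. It does not make the tests right for the design, because the price is power for modest effects.

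A reader might go further and infer that the plan will produce many false positives, because the ANOVA sentence speaks of recordings and features are extracted from one-sentence files. The documents do not support that. The last sentence points the other way, and neither the number of recordings per segment nor the person-by-condition variance is given. Inflation is possible only under the less likely reading, and its size cannot be stated.

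A second fair objection concerns the replacement. Signed-rank and repeated-measures ANOVA drop anyone with a missing condition. Section III expects up to 25 people to enter the main study for 20 completers, and Section VI intends to use all available data in its mixed models. This stands, and it is why a mixed model should lead.

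**Conclusion.** The concern holds in a limited form. The two named tests do not match the within-person design, and no other part of Section VI corrects this for voice features. On segment averages with positive within-person correlation, both tests are conservative. For a 0.5 SD shift at correlation 0.3 to 0.7, Mann-Whitney gives up about 13 to 52 power points against signed-rank (42 − 29 and 76 − 24).

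The mismatch is certain from the text. The sizes rest on assumed correlations, normal data, 5% alpha and 20 people with voice data. The conservative direction also needs one value per person per condition; two baselines entered as separate rows can weaken or, at the extreme, reverse it.

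Importance is low: no alpha or power is claimed for Aim 8, and the three primary outcomes are analysed by other, paired methods. It would be wrong to read the point as a threat to the trial's main conclusions.

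**What to change.** In the Aim 8 paragraph of Section VI:

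1. State that the tests use one segment-averaged value per person per segment.
2. Replace one-way ANOVA and Mann-Whitney U with a linear mixed model with random subject and fixed condition and period on all four segment averages, followed by pairwise condition contrasts. Keep each baseline as a separate observation in its own period. Code period with two levels: first baseline with first intervention, second baseline with second intervention. That gives four columns of rank 4. A merged baseline with its own period level is aliased with condition (five columns, rank 4), and so is a four-level code for segment position (six columns, rank 5). The model uses all available data, in line with the opening of Section VI.
3. For clearly non-normal features, add the Wilcoxon signed-rank test on within-person differences as a complete-pairs sensitivity analysis, and say how the baseline value is formed, for example as the mean of the two baseline segments.
4. If list-level or sentence-level values are analysed, add a person-by-segment random term.
5. Label the per-feature results exploratory and report the number of tests.

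The three-condition comparison stays, with the same data and no added procedures. There are costs. Per-feature false positives rise from below nominal to about 5%. The signed-rank test loses 1 to 2 power points against Mann-Whitney at zero correlation and drops people with a missing condition.
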